#### **Secondary efficacy endpoints**

The secondary efficacy endpoints for this study are mini-Rhinitis Quality of Life Questionnaire (RQLQ) and safety assessment. Serum will also be stored to evaluate changes in IgE and IgG subclasses.

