## **2.0 STUDY REFERENCE INFORMATION**

### **2.1 Endpoints**

#### **2.1.1 Primary Endpoints**

The primary endpoint is to quantify and compare the clinical difference in signs and symptoms and medication usage that may be apparent when subjects with active perennial allergic rhinitis (PAR) with or without seasonal symptoms (SAR) are treated in a double-blind, prospective, controlled eight weeks study with a PMA versus placebo.

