#### **12.1.1 Analysis Sets**

All efficacy and safety analyses will be analyzed using the full analysis set (FAS). The FAS will consist of all subjects who were randomized and received at least one dose of double-blind study immunotherapy. Efficacy analyses will be analyzed according to the treatment received and safety analyses will be analyzed according to the actual treatment received.

Unless otherwise specified, all statistical tests and confidence intervals will be two-sided and conducted at the 0.05 significance level.

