#### **12.1.3 Efficacy Analysis**

The intent-to-treat approach will be used. Baseline characteristics will be described using mean and standard deviation for continuous variables and medians and ranges for discrete variables. The primary efficacy variable of comparing PMA versus placebo will be undertaken by quantifying the instrument-assessment scores of each study subject in each of the two therapeutic arms of the investigation. The p-value, least square (LS) treatment means, difference between the LS treatment means, and 95% confidence intervals for the treatment differences will be presented. The success of blinding will be assessed by asking the patient and staff which treatment set they thought they were getting, i.e. active treatment or placebo. The results will be recorded at each study visit.

Total Nasal Symptoms Score (TNSS) and the Mini-RQLQ attached in Appendix F will be used to evaluate clinical efficacy. TNSS along with rescue medication use is recorded at home on a daily

card as shown in Appendix K. Daily scores will only be recorded on weeks 2, 10, and 14. The mini-RQLQ will be recorded in person at screening, during each study visit, and at followup. The correct use of the TNSS survey is to score 0-12 based on symptoms reported that day while the mini-RQLQ is scored 0-84 based on symptoms reported over the past week. Higher scores indicate worse symptoms.

The primary outcome measure is the average daily combined score (DCS) which is calculated by adding the average TNSS + average medication score as well as the mini-RQLQ at weeks 2,10 and 14.

Secondary outcomes will include the adverse events rate and TNSS between both groups using a one-tailed Fischer's exact test and/or unpaired t test.

Other outcomes include baseline characteristics, use of epinephrine, and drop out between both treatment groups I and II using a one-tailed Fischer's exact test and/or unpaired t test. Trend tests for comparison of both groups will be performed such as the Jonckheere-Terptsra trend test. A sum of Mann-Whitney-Wilcoxon tests may also be sensitive and reveal a mild trend. Other trend tests may also be used.

A Kaplan-Meier or similar product limit estimator function will also be used to calculate the effect of treatment over time.

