## **STUDY OVERVIEW**

### **Endpoints**

#### **Primary Endpoints**

The primary endpoint is to quantify and compare the clinical difference in signs and symptoms and medication usage as well as the global RQLQ index that may be apparent when subjects with active perennial allergic rhinitis (PAR) with or without seasonal symptoms (SAR) are treated in a double-blind, prospective, controlled eight weeks study with a proprietary mixture of FDA approved allergens (PMA) versus placebo.

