In this study approximately 36 study subjects will be equally randomized to active PMA or placebo. The duration of active PMA or placebo treatment will be 8 weeks with clinic visits twice-weekly during this period and a post-treatment safety follow up assessment at one month following the final administration of immunotherapy. All doses of immunotherapy will be administered in the study site clinic by the investigators or their designees.

A schematic of the study design is included in the Figure below. A schedule of assessments is listed in **Error! Reference source not found.** of the protocol.

Figure Schematic of Study Design

The SAP will follow the study protocol sections 12.1 to 12.3. Statistical methodology was developed in conjunction with the faculty of the Johns Hopkins Bloomberg School of Public Health Department of Biostatistics. Specific calculations include the following wherein "p" values as well as 95% confidence intervals will be calculated.

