### Primary Outcomes

1. Daily Combined Score (DCS) – Comparison of the delta visit 2 to visit 17 (change in score) between both treatment groups I and II using an unpaired t test.
2. Daily Combined Score (DCS) – Comparison of the delta visit 2 to visit 18 (change in score) between both treatment groups I and II using an unpaired t test.
3. mini-rhinoconjunctivitis quality of life questionnaire (RQLQ) - Comparison of the delta visit 2 to visit 17 (change in score) between both treatment groups I and II using an unpaired t test.
4. mini-RQLQ - Comparison of the delta visit 2 to visit 18 (change in score) between both treatment groups I and II using an unpaired t test.

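### The SAP sets four equal primary tests with no success rule, and the documents disagree on whether mini-RQLQ is primary

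*Combined protocol and SAP*

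**What the plan says.** **The tests.** The SAP's Primary Outcomes section numbers four unpaired t tests: DCS to visit 17, DCS to visit 18, mini-RQLQ to visit 17, and "mini-RQLQ - Comparison of the delta visit 2 to visit 18 (change in score) between both treatment groups I and II". It does not say which one leads.

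**The level.** The SAP gives no alpha of its own. It states that "The SAP will follow the study protocol sections 12.1 to 12.3", and protocol 12.1.1 states: "Unless otherwise specified, all statistical tests and confidence intervals will be two-sided and conducted at the 0.05 significance level". Nothing different is specified for these four tests. The SAP does set test-level rules elsewhere: it makes several secondary and other comparisons one-tailed.

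**The role of mini-RQLQ.**
- SAP, Primary Endpoints: primary. The aim is to "quantify and compare the clinical difference in signs and symptoms and medication usage as well as the global RQLQ index".
- Protocol 12.1.3: grouped with the primary outcome. The average DCS is named as the primary measure and is "calculated by adding the average TNSS + average medication score as well as the mini-RQLQ at weeks 2,10 and 14". The secondary outcomes that follow are adverse events and TNSS only.
- Protocol synopsis (1.2) and 4.1.2: secondary. "The secondary efficacy endpoints for this study are mini-Rhinitis Quality of Life Questionnaire (RQLQ) and safety assessment".
- Protocol 2.1.2: secondary, as the global RQLQ index. Section 2.1.1 leaves it out of the primary: "The primary endpoint is to quantify and compare the clinical difference in signs and symptoms and medication usage".

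**The role of DCS.** It is the primary assessment in the synopsis and in protocol 4.1.1, and it is on the SAP's primary list. The synopsis's Statistical Considerations place the primary variable at the end of study drug administration.

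**The concern.** With four equal primary tests and no success rule, the plan does not say which pattern of results makes the trial positive. Suppose mini-RQLQ is significant and DCS is not. The SAP's list would allow that to be reported as a primary success, while protocol 2.1 and 4.1 would call it a missed primary with a secondary finding. Both reports could cite the documents.

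Two further things are at stake. Counting any single significant test as success raises the false-positive rate above 0.05. And the sentence in 12.1.3 can be read as adding mini-RQLQ (0-84) to TNSS (0-12) and the medication score, which would change what DCS measures.

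**Working it through.** **1. The plan's own figure.** The documents state no family-wise error. Their only calculated figure is the sample size: 80% against 30% response, alpha 0.05, power 80%, total 28. With pooled variance and a two-sided test,

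n per arm = [1.960·√(2·0.55·0.45) + 0.842·√(0.8·0.2 + 0.3·0.7)]² / 0.5² = (1.379 + 0.512)² / 0.25 = 14.3.

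Rounded up this is 15 per arm, total 30, within two of the stated 28; power at 14 per arm is 79.1%. The figure reproduces closely. It rests on a responder rate, which is none of the four primary tests, so it does not show which of them is meant to lead.

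**2. Error if any one test counts.** If independent: 1 − 0.95⁴ = 18.5%. The four tests share subjects, so they are correlated. The documents give no correlations, so a range is assumed: the first number is between instruments at one visit, the second between visits within one instrument, and their product across both. Each setting used 200,000 simulated trials with no true effect, pooled t tests and 14 per arm (28/2).

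| Instrument/time correlation | Any one, two-sided | Any one, favouring PMA | All four |
|---|---|---|---|
| 0.3/0.5 | 17.1% | 8.6% | 0.0% |
| 0.5/0.7 | 15.1% | 7.5% | 0.2% |
| 0.7/0.8 | 12.9% | 6.5% | 0.5% |
| 0.9/0.9 | 9.9% | 5.0% | 1.6% |
| 0.95/0.9 | 9.1% | 4.5% | 1.9% |

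A single test gives 5% two-sided and 2.5% favouring PMA. At 18 per arm (36/2) the any-one column agrees within 0.2 percentage points.

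**3. How often the missing rule matters if PMA works.** Assume that all four outcomes carry a 1.10 SD effect. This gives 80% power per test at 14 per arm (noncentral t, 26 df, noncentrality 1.10·√(14/2) = 2.91). Mixed means at least one but not all four significant. Holm's first step compares the smallest p with 0.05/4 = 0.0125.

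| Correlation | Mixed, 14 per arm | Mixed, 18 per arm | All four significant, 14 per arm | Holm first step, 14 per arm |
|---|---|---|---|---|
| 0.3/0.5 | 48.2% | 30.3% | 50.3% | 91.8% |
| 0.5/0.7 | 40.1% | 25.3% | 56.4% | 86.6% |
| 0.7/0.8 | 32.3% | 20.8% | 61.6% | 81.4% |
| 0.9/0.9 | 20.6% | 13.3% | 69.0% | 73.8% |

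The narrower pattern, mini-RQLQ significant at one visit or both with DCS significant at neither, is much rarer: about 3-8% at 14 per arm and 2-4% at 18 per arm, over correlations up to 0.95/0.9.

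**The case against.** The strongest reply is that the documents do point somewhere. Protocol 4.1.1 calls DCS the primary assessment, the synopsis puts the primary variable at the end of treatment, and the SAP lists DCS at visit 17 first. A reader might infer from the SAP that no lead exists anywhere, but that goes too far: the protocol names DCS. What stands is that the SAP's list gives DCS no precedence, and position in a numbered list is not a testing order unless the plan says so.

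A reader might also infer that the SAP promoted an outcome that the protocol treats only as secondary. The documents do not support that. Section 12.1.3, which the SAP says it follows, groups mini-RQLQ with the primary outcome, so the conflict lies inside the protocol as well as between the documents.

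Third, the error figures depend on an any-one-wins rule that no document states and on correlations that no document gives. That is correct. The 9-17% also counts false differences favouring placebo, so the figure for a false claim of benefit is 5-9%.

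Finally, this is a small phase 2 proof-of-concept trial. That is a fair reason not to demand a full testing hierarchy. It is not a reason to leave the success criterion open.

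**Conclusion.** The point holds and should be fixed before the data are unblinded. There are four unranked primary tests, each at two-sided 0.05, with no adjustment or success rule, and the documents conflict on the role of mini-RQLQ. That much comes from the text alone.

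The size is conditional. Under an any-one-wins reading, two-sided family-wise error is about 9-17% and false wins for PMA about 5-9% against 2.5%, for assumed correlations of 0.3-0.95. Under an all-four reading error stays below 2%, but power is only 50-69% at 14 per arm when every outcome carries a 1.10 SD effect.

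It would be tempting to say that mixed results are likely and that the missing rule would often decide the conclusion. The calculations do not support that. Every mixed-result figure is below 50%, falling to 13-30% at 18 per arm, and many of those patterns include a significant DCS. The sharpest conflict, mini-RQLQ without DCS at either visit, arises in about 3-8% of trials at 14 per arm and 2-4% at 18. The 1.10 SD effect is itself an assumption, chosen to give 80% power per test.

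**What to change.** Before database lock and unblinding, name one primary outcome at one time point, tested at two-sided 0.05, and make the other three secondary. DCS change to visit 17 is the natural candidate, given the synopsis and protocol 4.1.1, but the choice is the sponsor's. If all four are kept as primary, state Holm.

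Then align protocol 1.2, 2.1, 4.1 and 12.1.3 with the SAP. In 12.1.3, state that DCS is mean TNSS plus mean medication score and that mini-RQLQ is analysed separately.

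**Cost.** Wording only. The SAP's introduction allows revisions before database lock, and protocol 12.1 requires the SAP to be final before unblinding.
- Single primary: keeps 80% power for a 1.10 SD effect at 14 per arm. In exchange, an effect on mini-RQLQ alone no longer counts as primary success, and the visit 18 comparison is no longer a primary claim if visit 17 is chosen.
- Holm: at 14 per arm, first-step power for a 1.10 SD effect is 59% if only one outcome carries it, 68-77% if both mini-RQLQ time points do, and 74-92% if all four do (correlations 0.9/0.9 to 0.3/0.5).

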## **Secondary Outcomes**

1. Total nasal symptoms score (TNSS)- Comparison of the delta visit 2 to visit 17 (change in score) between both treatment groups I and II using an unpaired t test.
2. TNSS - Comparison of the delta visit 2 to visit 18 (change in score) between both treatment groups I and II using an unpaired t test.
3. Adverse Events - Adverse events (AEs) were to be spontaneously reported or elicited during open-ended questioning, examination, or evaluation of a patient. Comparison of the rates of adverse events between both treatment groups I and II will be evaluated using a one-tailed Fischer's exact test.

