## **Other Comparisons and Outcomes**

1. Baseline characteristics - Comparison of the rates of specific characteristics between both treatment groups I and II using a one-tailed Fischer's exact test and/or unpaired t test.
2. Use of epinephrine - Comparison of the rates of epinephrine rescue medication use between both treatment groups I and II using a one-tailed Fischer's exact test.
3. Mini-RQLQ - Kaplan-Meier or similar repeated measures test will also be used to calculate the effect of treatment over time between both groups I and II.
4. Drop out - Comparison of the drop out rates between both groups I and II using a one-tailed Fischer's exact test.
5. Trend tests - For these study data, representing a continuous response, an appropriate test, such as the Jonckheere-Terptsra trend test, based on a sum of Mann-Whitney-Wilcoxon tests may be sensitive and reveal a mild trend where pair-wise comparisons may not be able to find significant differences and not be as helpful. Other trend tests may also be used.

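### Adverse events, epinephrine use and drop-out are to be compared with one-tailed Fisher tests whose direction is never stated, so the plan does not fix the p-value

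*Combined protocol and SAP*

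**What the plan says.** Protocol 12.1.1 sets the default: "Unless otherwise specified, all statistical tests and confidence intervals will be two-sided and conducted at the 0.05 significance level". The SAP, at the end of Study Design and Methods, says it follows protocol sections 12.1 to 12.3 and promises p-values with 95% confidence intervals.

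The exceptions are these:

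- **Adverse events.** SAP, Secondary Outcomes, item 3: the comparison of rates "will be evaluated using a one-tailed" Fisher's exact test. Protocol 12.1.3 lists as secondary outcomes "the adverse events rate and TNSS between both groups using a one-tailed" Fisher test and/or an unpaired t test.
- **Epinephrine use.** SAP, Other Comparisons and Outcomes, item 2: "Comparison of the rates of epinephrine rescue medication use between both treatment groups I and II using a one-tailed Fischer's exact test".
- **Drop-out.** SAP, same section, item 4: "Comparison of the drop out rates between both groups I and II using a one-tailed Fischer's exact test". Protocol 12.1.3 covers epinephrine use and drop-out in the same way.

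None of these places says which group is expected to have the higher rate, what alpha applies, or why one tail is used. Protocol 7.1 says that the active and placebo vial sets are labelled I or II at random, so the labels carry no direction.

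The protocol summary (Statistical Considerations, Efficacy Analyses) also plans a Fisher test of the percentage of subjects stopping for intolerance or lack of efficacy. No tail is given there, so the two-sided default applies.

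**The concern.** A one-tailed test is defined only once its tail is named. As written, two analysts could both follow the SAP and report p-values at opposite ends of the scale for the same table.

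The documents give no ground for assuming a direction. Active treatment may cause local swelling, but the placebo deliberately contains histamine, which is expected to cause mild itch in about 20% of control subjects (protocol 7.1). Subjects may stop for intolerance or for lack of efficacy, and these reasons could plausibly push drop-out in opposite directions between the arms.

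Two failures are possible. If the tail is fixed one way, an excess in the other arm cannot be flagged. If it is left open until the data are seen, the error rate of the comparison rises. Adverse events are a named secondary outcome, and the SAP's study overview lists drop-out rates and the adverse event profile as secondary endpoints.

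**Working it through.** **Inputs.** Recruitment of up to 36 subjects, 1:1, hence 18 per arm (protocol 12.3, 5.1). The calculated need is 28, or 14 per arm (12.3). Alpha is 0.05 (12.1.1). The documents give no expected counts for these comparisons, so the counts and event rates below are illustrative. The plan states no figure for these tests that could be reproduced.

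**One table, three p-values.** With 18 per arm and 10 events in total, the number X in the first arm follows, under no difference, P(X = k) = C(18,k) × C(18,10−k) / C(36,10), where C(36,10) = 254,186,856.

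For 8 versus 2 events:

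- Upper tail, P(X ≥ 8): (6,694,974 + 875,160 + 43,758) / 254,186,856 = 7,613,892 / 254,186,856 = 0.030.
- Lower tail, P(X ≤ 8): 0.996.
- Two-sided: 2 × 0.02995 = 0.060, because the distribution is symmetric when the arms are equal.

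Other tables at 18 per arm:

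| Events | Tail matching the data | Opposite tail | Two-sided |
|---|---|---|---|
| 5 vs 0 | 0.023 | 1.000 | 0.045 |
| 6 vs 1 | 0.044 | 0.996 | 0.088 |
| 10 vs 4 | 0.043 | 0.992 | 0.086 |

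The one-tailed p in the observed direction is exactly half the two-sided p for every table with unequal counts at 18/18 and at 14/14. With unequal arms the ratio runs from about 0.5 to 1. At 19/17, 8 versus 2 gives 0.047 against 0.065 (ratio 0.72), and 0 versus 5 gives 0.016 both ways (ratio 1.00).

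**Error rate if the tail is chosen after the data are seen.** For a common event rate π and n per arm, the exact error is the sum over all (x, y) of b(x; n, π) × b(y; n, π) × 1[p(x, y) ≤ 0.05], where b is the binomial probability. For the chosen-tail case, p is the smaller of the two one-tailed values. At n = 18:

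| Event rate | Two-sided Fisher | Tail chosen afterwards |
|---|---|---|
| 20% | 2.0% | 4.0% |
| 30% | 2.2% | 4.9% |
| 50% | 2.9% | 6.5% |

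The ratio is about 1.9 to 2.3 over this range. At n = 14 the chosen-tail error did not exceed about 4.2% at any rate tried from 5% to 50%.

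**Consistency within the plan.** A two-sided 95% interval does not correspond to a one-tailed test at 0.05. In the 8 versus 2 table, a one-tailed p of 0.030 would be called significant, while an interval obtained by inverting the two-sided Fisher test (p = 0.060) would include no difference. Subjects who stop for intolerance or lack of efficacy also overlap with drop-outs, so overlapping data would be tested two-sided under the protocol summary and one-tailed under 12.1.3 and the SAP.

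**The case against.** The strongest reply is that 12.1.1 begins with an allowance for exceptions, and both the protocol and the SAP specify the one-tailed tests. That is right. A reader might infer that the plan breaks its own two-sided rule, but the text does not support this. The exception is permitted; what it lacks is a direction and a reason.

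A reader might also infer that the safety p-values are simply halved. That holds only with equal arms and only if the tail matches the observed difference. In the other tail p is close to 1, and with unequal arms the reduction can vanish. A tail fixed towards harm would make a harm signal easier to flag, so smaller p-values are not in themselves the danger.

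Nor does the open tail generally push the error above 5%. Fisher's test is conservative at this size. The documents put local reactions at no more than about 20% in active subjects and itch at about 20% in controls; at that rate even a tail chosen afterwards gives 4.0%. The rate for any adverse event could be higher, but the documents do not state it.

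It can also be said that little rests on these tests. The safety analysis in 12.1.4 is descriptive, epinephrine use may produce no events, and the SAP analyses drop-out under other comparisons. The SAP's primary outcomes use t tests with no tail stated, so they are two-sided by default and unaffected. This limits the consequences, but it does not supply the missing direction.

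**Conclusion.** The point holds as a defect of specification that should be corrected. For adverse events, epinephrine use and drop-out, the stated rule does not determine a p-value. It is either open to choice after the data are seen or blind to an excess in one arm. It also fits poorly with the planned 95% intervals and the untailed Fisher test in the protocol summary.

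In the 8 versus 2 example the result ranges from 0.030 to 0.996, against 0.060 two-sided. Choosing the tail afterwards roughly doubles the error of the two-sided Fisher test at 18 per arm for event rates of 20% to 50%. It passes 5% only at the higher rates in that range. These figures assume 18 per arm and illustrative counts and rates; the lack of a stated direction depends on neither. The sample size and the primary comparison are not affected.

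**What to change.** In protocol 12.1.3 and in the SAP (Secondary Outcomes item 3; Other Comparisons and Outcomes items 2 and 4), replace *one-tailed* with *two-sided* Fisher's exact test for adverse events, epinephrine use and drop-out. Report each risk difference with its two-sided 95% confidence interval. State in the protocol summary that the test of stopping for intolerance or lack of efficacy is two-sided, so that it agrees with 12.1.1 and with the drop-out test.

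If the sponsor prefers to keep one tail, the minimum is to state the direction by treatment (active or placebo, not set I or II), the alpha and the reason for each outcome before unblinding.

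The cost is wording only, and the SAP allows revisions before database lock. Some p-values will be larger: at 18 per arm with one event in one arm, 7 events in the other are needed for p ≤ 0.05 instead of 6. Whether baseline characteristics should be tested at all is a separate question that this change need not settle.
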